#### **6.3.2.1. Unblinding**

The IRT will be programmed with blind-breaking instructions. In case of an emergency, the investigator has the sole responsibility for determining if unblinding of a participants' IMP assignment is warranted. Participant safety must always be the first consideration in making such a determination. Unblinding for any other reason will be considered a protocol deviation. If the investigator decides that unblinding is warranted, the investigator should make every effort to contact the sponsor prior to unblinding a participant's IMP assignment unless this could delay

emergency treatment of the participant. If a participant's IMP assignment is unblinded, the sponsor must be notified within 24 hours after breaking the blind. The date and reason that the blind was broken must be recorded in the source documentation and eCRF, as applicable.

Sponsor safety staff may unblind the IMP assignment for any participant with an SAE. The study team will remain blinded to IMP assignment. If the SAE requires that an expedited regulatory report be sent to one or more regulatory agencies, a copy of the report may be sent to investigators in accordance with local regulations and/or sponsor policy. Reason for unblinding and date must be recorded/documentated appropriately per study documentation process.

#### **6.4. Study Intervention Compliance**

When participants are dosed at the site, they will receive IMP directly from the investigator or designee, under medical supervision. The date and time of each dose administered in the clinic will be recorded in the IMP dosing eDiary. The dose of IMP and study participant identification will be confirmed at the time of dosing.

Compliance with IMP will be reviewed during phone visits by direct questioning and review of completed IMP dosing eDiary. However, IMP compliance cannot be fully assessed during phone visits since bottle(s) will not be returned. Possible deviation(s) from the prescribed dosing regimen should be discussed with the caregiver (eg, re-training provided) and documented in the source documents.

Compliance with IMP will be assessed at each visit where IMP is returned, as part of accountability assessment. Compliance will be assessed by direct questioning, counting returned bottle(s), review of completed IMP dosing eDiary, measurement of the IMP used from each bottle compared to expected usage, etc. during the site visits and documented in the source documents and eCRF. Significant deviation(s) from the prescribed dosage regimen should be recorded as protocol deviations as outlined within the pharmacy manual.

A record of the quantity of IMP dispensed to and administered by each participant must be maintained and reconciled with IMP and compliance records. IMP start and stop dates, including dates for IMP dosing delays and/or dose adjustments, will also be recorded.

#### **6.5. Dose Modification**

Body weight will be used to calculate the IMP dose. Body weight will be confirmed prior to IMP dose calculation. If a visit is being done at home, the last available clinic weight will be used to calculate the dose.

Refer to the "CBD Dose Adjustment" section of the current approved GWP42003-P IB for detailed information regarding potential drug interactions and associated dose modifications.

##### **Part A:**

On Day 1 (Visit 3) of treatment with IMP, participants will be initiated on a dose of 2.5 mg/kg BID (5 mg/kg/day), and after 1 week, the dose will be increased to 5 mg/kg BID (10 mg/kg/day) at the Day 8 (Visit 4) phone visit.

For participants who are tolerating the IMP at 5 mg/kg BID (10 mg/kg/day) and require further reduction of seizures, investigators may choose to increase their dosage up to a maximum dosage

of 10 mg/kg BID (20 mg/kg/day). The decision to titrate above 5 mg/kg BID (10 mg/kg/day) should be based on the observed efficacy, safety, and tolerability of the participant (including review of laboratory values) per the clinical judgement of the investigator.

Starting at the Day 15 (Visit 5) phone visit, investigators have the option to titrate participants no more rapidly than every 7 days by an additional 2.5 mg/kg BID (5 mg/kg/day) up to a maximum daily dosage of 20 mg/kg/day. The investigator will determine if further dose adjustments are warranted during unscheduled phone visits and/or scheduled phone or clinic visits throughout the remainder of the 14-week treatment period. If dose change is warranted outside of a scheduled visit, the caregiver should be contacted by phone prior to making any dose increases above 10 mg/kg/day to assess the appropriateness of the dose increase based on the participant's reported clinical response and ensure the caregiver has received the updated dosing schedule reflecting the new target dose. This contact should be documented as an unscheduled phone visit in the eCRF.

After the Day 15 (Visit 5) phone visit, if in the investigator's opinion, a participant is experiencing a clinically meaningful improvement in EMAS-associated seizures, the investigator can choose to continue treatment at the participant's current dosage and may re-consider an increase in the dosage of IMP at either a later study visit, or at any time between study visits, as described above.

If a participant reports any tolerability issues related to IMP, the investigator can also decrease a participant's current dosage. Dose decreases to below 10 mg/kg/day, based on safety and tolerability may occur at any time. The caregiver should be contacted by phone prior to making any dose decreases below 10 mg/kg/day. Investigators should regularly monitor a participant's response to treatment and re-evaluate the need for adjustments to dosage (ie, increase, maintain, or decrease) at the next study visit, if applicable. Dose decreases below 10 mg/kg/day may occur in decrements of 2.5 or 5 mg/kg/day based on the clinical judgment of the investigator.

**Table 4: Possible Range of Investigational Medicinal Product Doses During the 14-Week Treatment Period of Part A**

Day	Morning Dose (mg/kg)	Evening Dose (mg/kg)	Total Daily Dose (mg/kg/day)
1-7	2.5	2.5	5
8-14	5	5	10
15-21	5 or 7.5	5 or 7.5	10 or 15
22-56	5, 7.5, or 10*	5, 7.5, or 10*	10, 15, or 20*
57-84	5, 7.5, or 10*	5, 7.5, or 10*	10, 15, or 20*
85-98	5, 7.5, or 10*	5, 7.5, or 10*	10, 15, or 20*

\* The maximum dosage (or dosage equivalent) that could be administered by this point or subsequent points.

Note: The dose ranges in the table serve as guidance only. Slight differences in dosage timing are allowed.

At the End of Treatment visit for Part A, participants who complete the treatment period, continue to meet all Part B eligibility criteria, and for participants whom the investigator feels continued treatment in an extension trial represents a favorable risk-benefit assessment for the participant will be offered the option to enroll in Part B.

## Part B

Participants eligible to participate in Part B of the study will not be required to complete the Part A taper period (Visit 10) or follow-up visit (Visit 11). The Part A end of treatment visit (Visit 9) procedures/data should be utilized for Visit 1 of Part B (ie, the same procedures should not be repeated at Visit 9 of Part A and Visit 1 of Part B). If the participant is continuing to Part B, the IMP should only be dispensed at Part B Visit 1. If the participant is not continuing to Part B, the IMP for the taper period will be dispensed at Part A Visit 9, as required.

In order to maintain consistent exposure to IMP and maintain the integrity of the blind, participants will enter a 2-week blinded titration (or transition) to Part B. Part B IMP will be increased to 10 mg/kg/day whilst blinded IMP is simultaneously tapered down to zero. If a participant completes Part A on a dose < 10 mg/kg/day and continues into Part B, they can transition to Part B and remain at a lower GWP42003-P dosage following approval from the medical monitor and/or sponsor representative. After Week 2 (Visit 3), investigators will then have the option to titrate participants no more rapidly than every 7 days by an additional 2.5 mg/kg BID (5 mg/kg/day) up to a maximum daily dosage of 20 mg/kg/day ([Table 5](#)).

After Week 2 (Visit 3), it is recommended that the GWP42003-P dosage should be increased no more rapidly than 5 mg/kg/day (2.5 mg/kg BID) every 7 days. However, for some participants in whom a more rapid titration from 10 to 20 mg/kg/day is warranted, the dosage may be increased no more frequently than every other day following consultation with the medical monitor and/or sponsor representative.

If any safety/tolerability issues, investigators can decide to maintain or decrease dosage.

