**Part B:**

- Part B will evaluate the long-term safety, tolerability, [REDACTED] of GWP42003-P for a period of 48 weeks in participants with EMAS-associated seizures. All participants in Part B will receive GWP42003-P.
- The duration of study for Part B will be approximately 54 weeks, which includes a 48-week treatment period (including a 2-week blinded titration [or transition] period for all participants), 10-day taper period, and a safety follow-up period (4 weeks after end-of-taper visit).
- Part B will be available to participants who complete Part A of the study and continue to meet all eligibility criteria and to participants for whom the investigator feels continued treatment in Part B represents a favorable risk-benefit assessment.
- Participants who continue into Part B of the study will proceed without the Part A taper period (Visit 10) and follow-up visit (Visit 11). The Part A end of treatment visit (Visit 9) procedures/data will then be utilized for Visit 1 of Part B (ie, the same procedures should not be repeated at Visit 9 of Part A and Visit 1 of Part B). If the

participant is continuing to Part B, IMP should only be dispensed at Part B Visit 1. If the participant is not continuing to Part B, IMP for the taper period will be dispensed at Part A Visit 9, as required.

- Participants who do not enroll in Part B at Visit 9 of Part A will be required to complete Part A and continue to an end-of-taper visit (Visit 10) and a follow-up visit (Visit 11).
- In order to maintain consistent exposure to IMP and maintain the integrity of the blind, participants will enter a 2-week blinded transition to Part B. Part B IMP will be titrated up to 10 mg/kg/day whilst blinded IMP is simultaneously tapered down to zero. All participants will complete the transition and enter Part B taking GWP42003-P ([Section 6.5 Part B](#)) ([Table 5](#)).
- A safety follow-up visit (phone call) will be conducted 4 weeks after the end-of-taper visit. If a participant withdraws from the study prematurely (ie, before the end of treatment visit), an early withdrawal visit will be conducted, and a safety follow-up phone call will occur 4 weeks after their last dose of IMP. Participants who discontinue IMP prematurely should be encouraged to complete the end of treatment visit and taper period.

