#### **Part B:**

Participants not entering Part B or who discontinue IMP early will down-titrate over a period of 10 days. Participants eligible to enter Part B will enter the blinded transition period. Part B GWP42003-P will be titrated to 10 mg/kg/day whilst blinded IMP is simultaneously tapered down to zero. For participants who are tolerating IMP at 10 mg/kg/day and require further reduction of seizures, dose escalation up to a maximum daily dosage of 20 mg/kg/day may occur after Day 15 based on the investigator's assessment of safety and tolerability. The IMP dose may be increased by increments of 2.5 mg/kg BID (5 mg/kg/day) no more rapidly than every 7 days, up to a maximum daily dosage of 20 mg/kg/day.

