### **Part B:**

Part B will evaluate the long-term safety, tolerability, [REDACTED] of GWP42003-P for a period of 48 weeks in participants with EMAS-associated seizures. All participants in Part B will receive GWP42003-P.

The duration of study for Part B will be approximately 54 weeks, which includes a 48-week treatment period (including a 2-week blinded titration [or transition] period for all participants), 10-day taper period, and a safety follow-up period (4 weeks after end-of-taper visit).

Part B will be available to participants who complete Part A of the study and continue to meet all eligibility criteria and to participants for whom the investigator feels continued treatment in Part B represents a favorable risk-benefit assessment.

Participants who continue into Part B of the study will proceed without the Part A taper period (Visit 10) and follow-up visit (Visit 11). The Part A end of treatment visit (Visit 9) procedures/data will then be utilized for Visit 1 of Part B (ie, the same procedures should not be repeated at Visit 9 of Part A and Visit 1 of Part B). If the participant is continuing to Part B, IMP should only be dispensed at Part B Visit 1. If the participant is not continuing to Part B, IMP for the taper period will be dispensed at Part A Visit 9, as required.

Participants who do not enroll in Part B at Visit 9 of Part A will be required to complete an end-of-taper visit (Visit 10) and a follow-up visit (Visit 11).

In order to maintain consistent exposure to IMP and maintain the integrity of the blind, participants will enter a 2-week blinded transition to Part B. Part B IMP will be titrated up to 10 mg/kg/day whilst blinded IMP is simultaneously tapered down to zero. All participants will complete the transition and enter Part B taking GWP42003-P ([Section 6.5 Part B](#)) ([Table 5](#)).

Investigators have the option to titrate participants no more rapidly than 2.5 mg/kg BID (5 mg/kg/day) every 7 days, up to a maximum daily dosage of 20 mg/kg/day.

After Part B Week 2 (Visit 3), for some participants in whom a more rapid titration from 10 to 20 mg/kg/day is warranted, the dosage may be increased no more frequently than every other day following consultation with the medical monitor and/or sponsor representative.

If any safety/tolerability issues, investigators can decide to maintain or decrease dosage.

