### 6.2. Preparation/Handling/Storage/Accountability

The investigator or designee must confirm appropriate temperature conditions have been maintained during transit for all IMP received and any discrepancies are reported and resolved before use of the IMP.

Only participants randomized to receive IMP in the study may receive IMP and only authorized site staff may supply or administer IMP. All IMP must be stored in a secure, environmentally

controlled, and monitored (manual or automated) area in accordance with the labeled storage conditions with access limited to the investigator and authorized site staff.

For self-administration of IMP, participants/caregivers will be provided with bottle(s) containing the oral dosing solution along with oral syringes. Participants/caregivers will be trained, during Visit 3 at the study site, to self-administer IMP orally or with gastrostomy or nasogastric tubes BID (eg, morning and evening) preferably about the same time each day, consistently with or without food. Participants/caregivers will be provided with clear instructions for the dose escalation and taper dosing periods of the study via a printed dosing schedule and will record usage of IMP as part of the IMP dosing eDiary to aid in compliance.

Where required by local regulations, IMP may be dispensed more frequently than outlined in the schedule of assessments by completion of an unscheduled dispensing visit.

The investigator, institution, or the head of the medical institution (where applicable) is responsible for IMP accountability, reconciliation, and record maintenance (ie, receipt, reconciliation, and final disposition records).

Further guidance and information for the final disposition of unused IMP are provided in the pharmacy manual or other specified location.

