### **6.3.2. Blinding**

At the start of Part A, participants will be randomly assigned in a 1:1 ratio to receive GWP42003-P or matching placebo. Investigators will remain blinded to each participant's assigned IMP throughout the course of the study.

Participants entering Part B of the study, will first complete a 2-week blinded titration phase. Following the blinded titration phase, participants will start open-label treatment with GWP42003-P.

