**Table 5: Cross-Titration Scheme from End of 14-Week Treatment Period in Part A to Start of Part B**

Study Part/ Visit	Visit Type	Study Day	GWP42003-P 10 mg/kg/day			GWP42003-P 15 mg/kg/day			GWP42003-P 20 mg/kg/day			Placebo		
			Blinded (mg/kg/day)	OL (mg/kg/day)	Total Dose (mg/kg/day)	Blinded (mg/kg/day)	OL (mg/kg/day)	Total Dose (mg/kg/day)	Blinded (mg/kg/day)	OL (mg/kg/day)	Total Dose (mg/kg/day)	Blinded (mg/kg/day)	OL (mg/kg/day)	Total Dose (mg/kg/day)
Part A Visit 9	C	99	10	0	10	15	0	15	20	0	20	0	0	0
Part B Visit 1	C	1-7	5	5	10	10	5	15	15	5	20	0	5	5
Part B Visit 2	P	8-14	0	10	10	5	10	15	10	10	20	0	10	10
Part B Visit 3	P	15-21	-	10 or 15	10 or 15	0	10 or 15	10 or 15	5	10 or 15	15 or 20	0	10 or 15	10 or 15
Part B Visit 4	P	22-28	-	10, 15, or 20	10, 15, or 20	-	10, 15, or 20	10, 15, or 20	0	10, 15, or 20	10, 15, or 20	0	10, 15, or 20	10, 15, or 20

Abbreviations: C = clinic; OL = open-label; P = phone.

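### The text gives a 2-week blinded transition into Part B, but Table 5 keeps participants who finish Part A on 20 mg/kg/day on blinded product for 3 weeks

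*Combined protocol and SAP*

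**What the plan says.** Four places in the protocol describe the move into Part B as lasting 2 weeks.

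- Synopsis (1.1) and Section 4.1, Part B: the extension is a "48-week treatment period (including a 2-week blinded titration [or transition] period for all participants".
- Section 4.1, with matching text in the Synopsis: "participants will enter a 2-week blinded transition to Part B. Part B IMP will be titrated up to 10 mg/kg/day", while blinded product goes to zero over the same period. Both paragraphs end by pointing to Section 6.5 and Table 5.
- Section 6.3.2: the blinded phase lasts 2 weeks, and then "Following the blinded titration phase, participants will start open-label treatment with GWP42003-P".
- Section 6.5, Part B: "participants will enter a 2-week blinded titration (or transition) to Part B", again with blinded product going to zero as the Part B product reaches 10 mg/kg/day.

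Table 5 is the only step-by-step schedule for the blinded product. Its row for Part B Days 15-21 begins "Part B Visit 3 P 15-21 - 10 or 15 10 or 15 0 10 or 15 10 or 15 5 10 or 15". The entry of 5 is blinded product, in mg/kg/day, for participants who finished Part A on 20 mg/kg/day.

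On the speed of open-label titration after Week 2, Sections 4.1 and 6.5 allow an exception to the weekly limit for the step from 10 to 20 mg/kg/day: "the dosage may be increased no more frequently than every other day following consultation with the medical monitor and/or sponsor representative". The Synopsis gives only the weekly limit: "The IMP dose may be increased by increments of 2.5 mg/kg BID (5 mg/kg/day) no more rapidly than every 7 days".

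**The concern.** For one dose group, the length of the blinded taper depends on which part of the protocol is read. By the text, blinded product has stopped when Week 3 of Part B begins. By Table 5, it continues for another week.

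This is home dosing of children and adolescents. Caregivers work from a separate document: "Participants/caregivers will be provided with clear instructions for the dose escalation and taper dosing periods of the study via a printed dosing schedule". That schedule is not among the documents, so it is not known whether it follows the text or the table. Section 6.5 says that the transition exists to keep exposure consistent and to protect the blind, and the discrepancy touches both aims. Part B Visits 2 to 4 (Days 8, 15 and 22) are phone contacts. The next visit at which bottles are returned and dispensed is Visit 5, on Day 29.

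**Working it through.** **Inputs.** The stated length is 2 weeks, or 14 days (Sections 1.1, 4.1, 6.3.2 and 6.5). Daily doses come from Table 5, in mg/kg/day, as blinded + open-label = total.

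| Part B days | Finished Part A on 10 | Finished on 15 | Finished on 20 |
|---|---|---|---|
| 1-7 | 5 + 5 = 10 | 10 + 5 = 15 | 15 + 5 = 20 |
| 8-14 | 0 + 10 = 10 | 5 + 10 = 15 | 10 + 10 = 20 |
| 15-21 | none + (10 or 15) = 10 or 15 | 0 + (10 or 15) = 10 or 15 | 5 + (10 or 15) = 15 or 20 |
| 22-28 | none + (10, 15 or 20) = 10, 15 or 20 | none + (10, 15 or 20) = 10, 15 or 20 | 0 + (10, 15 or 20) = 10, 15 or 20 |

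**Step 1: is the table sound?** Every row adds up to its printed total, so the 5 on Days 15-21 is not a fault of text extraction. The blinded dose falls by 5 mg/kg/day each week from Part B Day 1. The number of weeks on blinded product should therefore be (final Part A dose / 5) - 1:

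- 10 mg/kg/day: 10/5 - 1 = 1 week, last blinded day 7
- 15 mg/kg/day: 15/5 - 1 = 2 weeks, last blinded day 14
- 20 mg/kg/day: 20/5 - 1 = 3 weeks, last blinded day 21

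All three agree with the table.

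**Step 2: does the stated 2 weeks reproduce?** It does for the 10 and 15 groups, whose blinded product is at zero by Day 15. It does not for the 20 group, which is still on 10 mg/kg/day of blinded product on Day 14. The gap is 21 - 14 = 7 days.

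**Step 3: dose on Days 15-21 in the 20 group.** Blinded product is 5 by the table and 0 by the text, a difference of 5 mg/kg/day. With Table 5's own open-label doses (10 or 15):

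- by the table: 5 + 10 = 15, or 5 + 15 = 20
- if blinded product had stopped at Day 14: 0 + 10 = 10, or 0 + 15 = 15

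The second line is not the full range that the text permits. The faster option could bring open-label product to 20 within that week: two steps of 5 mg/kg/day, if the usual step size applies, at least one day apart. Without blinded product the range is then 10 to 20.

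**Step 4: the faster option alongside blinded product.** With 5 mg/kg/day of blinded product and a total of at most 20, open-label product could be no more than 20 - 5 = 15 on Days 15-21, the highest value that Table 5 prints. The text does not state this limit or say how the two combine.

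**The case against.** The best reply is that the text is a summary and Table 5 is the detail. The Synopsis and Section 4.1 send the reader to Table 5, and part of the 2-week wording fits every column: open-label product reaches 10 mg/kg/day in Week 2, and further titration opens at Visit 3. This stands as context and confines the conflict to the blinded taper at one dose level. It does not remove the conflict. The text makes the blinded taper run alongside the 2-week rise, Section 6.3.2 puts open-label treatment after the blinded phase, and nothing says which source prevails. The note that doses are guidance only sits under Table 4, which covers Part A.

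Three stronger readings are tempting, and the documents do not support them.

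- **A fixed fall in dose.** Comparing 20 on Day 14 with 10 or 15 afterwards suggests a drop of 25% to 50% under the text. That calculation sets blinded product to zero inside Table 5's open-label column and leaves out the faster option, under which open-label product could reach 20. The text also gives no stepwise blinded schedule of its own.
- **A dose above the maximum.** Open-label 20 plus blinded 5 would be 25 mg/kg/day. This requires reading the maximum as open-label product alone, which no section says. It is written as a maximum daily dosage, Section 6.7 treats any amount of study product above 20 mg/kg in 24 hours as a possible overdose, and the faster option requires consultation.
- **Undetected misdosing.** Section 6.4 does say that phone visits cannot fully assess compliance, but they include direct questioning and review of the dosing eDiary. Phone contacts on Days 15 and 22 bracket the disputed week. Nothing shows that the caregiver schedule departs from Table 5.

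**Conclusion.** The inconsistency is real and limited. For participants who finish Part A on 20 mg/kg/day, the text gives 14 days of blinded product and Table 5 gives 21. The sources differ by 5 mg/kg/day of blinded product on Days 15-21, taking the text to mean that blinded product is at zero from Day 15. The 10 and 15 groups are consistent. Placebo participants on the volume matching 20 mg/kg/day are presumably affected too, because their blinded schedule must look the same. That is an assumption: the placebo column of Table 5 shows zeros for drug content and does not show volume.

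The unstated interaction between faster titration and continuing blinded product, and the Synopsis's silence on that option, are minor alignment points. No harm is claimed. The Part A 14-week treatment period is over by then, and the Part B key secondary efficacy endpoints are descriptive, so this is a matter of clear dosing instructions and the blind. It should be fixed.

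**What to change.** 1. Have the sponsor's clinical team decide the length of the blinded taper for participants finishing Part A on 20 mg/kg/day or the matching placebo volume. Then make Sections 1.1, 4.1, 6.3.2, 6.5 and Table 5 say the same thing, including when the blinded phase ends.
2. State in Sections 4.1 and 6.5 how the faster titration option applies while blinded product continues and how it relates to the 20 mg/kg/day maximum. Align the Synopsis with those sections.
3. Check the printed caregiver dosing schedule against the reconciled rule.

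The cost is wording changes and one document check. The Part A analysis and the sample size do not change.
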